#### **Sensitivity analyses.**

**Carryover effects for new-prescription alerts:** Primary analyses will be conducted as intent-to-treat analyses among prescriber-patient dyads for whom an alert was triggered. This allows investigation of the best types of alerts given the need for an alert. However, for new-prescription alerts, it is also possible that alerts that include the option for pharmacist referral vs. those that don't also differentially affect how many future DOAC prescribing errors are made. Specifically, prescriber-pharmacist collaboration may provide the prescriber with new knowledge about evidence-based DOAC prescribing that could be applied to future DOAC prescriptions, avoiding the occurrence of an alert altogether. To

explore these effects, we will also evaluate the main effect of the two new-prescription alerts on the proportion of DOAC patients that receive a new prescription for an evidence-based DOAC using the model described above, but including all patients to whom they prescribed a DOAC from the point they received their first new-prescription alert through the end of the 18-month study period. This will allow us to evaluate whether correct DOAC prescribing improved overall by type of new-prescription alert.

**Treatment-as-received analyses:** In line with intent-to-treat clinical best practices, prescribers will be randomized to both types of alerts at the time of their initial receipt of either type of alert. This approach was chosen for both good clinical practice and pragmatic reasons, but also with the support of our preliminary data, which showed that on one day, more than 1/4 of Michigan Medicine prescribers had one or more DOAC patients receiving a non-evidence-based prescription (see Power and Sample Size, above). There is a possibility that during trial period, some prescribers will only ever receive one type of alert, never exposed to their second randomized treatment—i.e., they made an initial prescribing error but never had a DOAC-receiving patient need a change in prescription, or vice versa. While we believe that this will be the case for only a minority of enrolled prescribers, sensitivity analyses will examine treatment-as-received effects and will re-assess main effects for the two factors including only patients for prescribers who received that type of alert.

**Changes in patient population:** While unlikely, it is also possible that a prescriber's patient panels may change directly or indirectly as a result of their assigned treatment. To account for this, sensitivity analyses will also rerun models including only patients that were affiliated with the prescriber prior to randomization.

---

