## 6 STUDY INTERVENTION

### 6.1 STUDY INTERVENTION(S) ADMINISTRATION

#### 6.1.1 STUDY INTERVENTION DESCRIPTION

The intervention consists of an EHR alert that is presented to prescribers at the time that they are prescribing a DOAC, OR a notification in the EHR that indicates that an existing prescription for a DOAC does not meet the prescribing guidelines (a potential medication error). Existing prescription notifications are triggered once daily through an EHR registry that is updated continuously.

The **alerts** were designed through a user-centered design process to ensure that they are clear and usable. There will be two versions of the alerts that are identical other than except for one aspect: One alert will include a 'button' to click to automatically get a pharmacy consult; one will not include such a button.

The **notifications** were designed through a user-centered design process to ensure that they are clear and usable. Alerts will be identical, but will be routed one of two ways:

1. They will be routed initially to a pharmacist, who may then contact the prescriber to request/recommend a prescription change.
2. They will be routed directly to the prescriber, who may change the prescription, contact a pharmacist, or opt to keep the prescription unchanged.

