## 9 STATISTICAL CONSIDERATIONS

### 9.1 SAMPLE SIZE DETERMINATION

This study is powered for our primary comparison, which is the comparison of our two different notifications. We will use mixed-effects binary logistic regression to model the proportion of inappropriate DOACs that are changed within 7 days following an alert.

We anticipate randomizing 300 prescribers to different notifications over the course of the study, allowing for a main effect comparison of 150 prescribers randomized to each of Notification A vs. B. This estimate for prescribers is pulled from 2019 preliminary data indicating Michigan Medicine had more than 1000 unique DOAC prescribers, and a one-day pull in February 2020 that indicated more than 250 prescribers on that day had one or more patients currently receiving an inappropriate DOAC, thus eligible for randomization to a longitudinal notification. For our secondary aim, examining the main effect of alerts, we also anticipate randomizing 300 prescribers to initial prescription alerts over the study period, or 150 to each of Alert 1 and Alert 2, respectively.

For our patient-level main effects analyses, we estimate that prescribers will average 2 patients that trigger an inappropriate DOAC alert over the 12-month trial period. As of June 14, 2022, Michigan Medicine currently has 11,590 patients receiving a DOAC. Pilot data indicates that about 40% of prescribers changed prescriptions following an notification that did not involve a pharmacist; notifications that did involve pharmacists resulted in change approximately 60% of the time. Using a base rate of 40% and assuming a patient  $n=600$ , alpha of 0.05 and prescriber-level ICC of 0.1, we will have 80% power to detect a difference in proportions of 0.12 (or 40% vs. 52%). Table 3 shows power for several other risk ratios, baseline rates, and number of patients per prescriber. All estimates were computed in Stata 17.

Table 3. Power Calculations (Prescriber N=300)

Table 3. Power Calculations (Prescriber N=300)				
Patient n=2	Base Proportion			
Risk Ratio	0.3	0.4	0.5	0.6
1.2	32%	47%	65%	84%
1.3	44%	63%	83%	96%
1.4	67%	87%	98%	>99%
1.5	84%	97%	>99%	>99%
1.6	94%	>99%	>99%	>99%
Patient n=3				
Risk Ratio				
1.2	42%	60%	79%	94%
1.3	74%	91%	99%	>99%
1.4	93%	>99%	>99%	>99%
1.5	>99%	>99%	>99%	>99%
1.6	>99%	>99%	>99%	>99%

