## 9.3 STATISTICAL ANALYSES

### 9.3.1 GENERAL APPROACH

The main effect analyses will allow us to determine the impact of different alert- and notification types on evidence-based DOAC prescribing in both newly prescribed DOAC prescriptions and existing DOAC prescriptions in order to understand under what contexts prescriber-pharmacist collaboration is an effective implementation strategy. In both our primary and secondary outcomes, our analyses will compare the main effects of each intervention, i.e., new prescription alerts (Alerts 1 vs 2) and existing-prescription notifications (Notifications A vs B), to determine which are most effective. For both interventions, the outcome of interest will be whether the patient whose prescription triggered the alert/notification (i.e., is receiving a non-evidence based DOAC) has their prescription changed following the alert or notification.

For the primary intervention outcome (existing-prescription notifications), main effect analyses will compare the proportion of patients receiving an evidence-based DOAC prescription within seven business days following the notification between prescribers randomized to receive the notifications themselves vs. prescribers for whom notifications were sent directly to anticoagulation clinic pharmacists.

For the secondary intervention outcome (new DOAC prescription alerts), main effect analyses will compare the proportion of patients receiving an evidence-based DOAC seven business days following the notification between prescribers randomized to receive enhanced alerts vs. enhanced alerts plus pharmacist referral.

The treatment interaction will allow evaluation of whether certain alerts and notifications work better when provided in tandem.

The main outcome analysis will use mixed-effects logistic regression models to account for the binary patient-level outcome variable of evidence-based DOAC receipt after an alert. The two treatment factors and their interaction will be included as fixed effects, as well as any stratification variables and baseline patient- and/or prescriber-level characteristics that are unbalanced. A prescriber-level random effect will account for patient clustering within prescribers, and an unstructured covariance matrix will be used for residual errors. Similar mixed-effects regression analyses will be conducted for secondary outcomes, adapted for different outcome measures or levels of analysis.

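### The carry-over analysis of new-prescription alerts mixes the alert's direct effect with any learning, so it cannot isolate carry-over if the two alerts differ in immediate correction

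*Combined protocol and SAP*

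**What the plan says.** The carry-over paragraph under Sensitivity analyses in Section 9.3.5 starts from the idea that collaboration with a pharmacist may teach prescribers something they use on later orders, "avoiding the occurrence of an alert altogether". To explore this, it compares the two new-prescription alerts on "the proportion of DOAC patients that receive a new prescription for an evidence-based DOAC using the model described above". The analysis set is widened from alerted patients to "including all patients to whom they prescribed a DOAC from the point they received their first new-prescription alert", up to the end of the 18 months. The paragraph closes by saying this will show whether correct prescribing got better in total by alert type.

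The model referred to is in Section 9.3.1, where the outcome is the "binary patient-level outcome variable of evidence-based DOAC receipt after an alert". Section 6.1.1 says the alert is "presented to prescribers at the time that they are prescribing a DOAC", so it can change the order that set it off. The Schedule of Activities (1.3) collects data at later alerts too, so the assigned alert goes on firing on later errors.

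Section 9.3.5 also plans an interrupted time series of new-prescription alerts per DOAC prescribed. It compares the study period with the 24 months before it, and no comparison of Alert 1 with Alert 2 is stated.

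**The concern.** Carry-over here is a statement about orders before any alert acts: does a prescriber in one arm make fewer errors at order entry than a prescriber in the other? The planned outcome looks at what the patient ends up with. An order that was wrong when entered and then corrected by the alert counts the same as an order that was right from the start.

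The direct effect of the alert, which the secondary endpoint measures, is therefore inside the carry-over outcome in two places. It acts on every later erroneous order, and it acts on the index order, which is an error by definition and which nothing in the text removes.

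At stake is what a difference in this analysis means. If the secondary endpoint favours one alert, this analysis will tend to favour it too, and the reader cannot tell whether prescribers learned anything.

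**Working it through.** **The plan's nearest figure.** The carry-over analysis has no stated power. Section 9.1 gives 80% power for 40% vs 52% with 300 prescribers, 2 patients each, ICC 0.1 and alpha 0.05 (two-sided assumed). Effective n per arm = 150 × 2 / (1 + (2 − 1) × 0.1) = 272.7, which gives 80.5%. The text figure reproduces. (Table 3 prints 63% for the same case, base 0.4 and risk ratio 1.3; that is a separate matter.)

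**Inputs.**
- Prescribers: Section 9.1 says "we also anticipate randomizing 300 prescribers to initial prescription alerts over the study period, or 150 to each of Alert 1 and Alert 2".
- Correction rates c0 = 0.40 and c1 = 0.60 (pilot), or 0.52 (the design difference), from Section 9.1. These are notification figures. Using them for alerts is an assumption.
- Error rate at order entry, e: assumed 7.2%, 10% or 20%. Section 2.1 gives 10–20% of prescriptions, and a local 7.2% that is a one-day prevalence among existing patients, not an order-entry rate.
- Later orders per prescriber, k: not in the documents; 5, 10 and 20 assumed.
- ICC 0.1 for corrections (Section 9.1) and 0.03 for errors (assumed; Section 9.1 uses 0.03 for clinical events).

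**No-learning case.** Both arms err at the same rate e. A later order ends evidence-based with probability 1 − e(1 − c), and the index order with probability c. The expected proportion is

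[k(1 − e(1 − c)) + c] / (k + 1) with the index order, and 1 − e(1 − c) without it.

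The arm difference is (c1 − c0)(1 + ke)/(k + 1) with the index order and e(c1 − c0) without it. Both are zero when c1 = c0 and are linear in the gap.

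**With e = 0.10 and k = 10:**
- c = 0.40: (10 × 0.94 + 0.40)/11 = 9.80/11 = 89.1%; without the index order, 94%.
- c = 0.60: (10 × 0.96 + 0.60)/11 = 10.20/11 = 92.7%; without the index order, 96%.
- Difference with the index order: 0.20 × 2/11 = 3.6 points, half of it from the index order.
- For 0.40 vs 0.52: 0.12 × 2/11 = 2.2 points with the index order, 0.10 × 0.12 = 1.2 points without.

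**How often this would reach p < 0.05.** Simulation with no learning: 150 prescribers per arm, beta-binomial errors and corrections, prescriber-level z-test, 3,000 runs per cell, over all nine combinations of e and k.

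| Scoring | 0.40 vs 0.60: difference (points) | p < 0.05 | 0.40 vs 0.52: difference (points) | p < 0.05 |
|---|---|---|---|---|
| After alert, index order in | 2.3–6.7 | 94–99.9% | 1.4–4.0 | 55–81% |
| After alert, index order out | 1.4–4.0 | 30–99% | 0.9–2.4 | 13–69% |
| As first entered, index order out | 0 | about 5% | 0 | about 5% |

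A random-intercept logistic model fitted to one cell (0.40 vs 0.60, e = 10%, k = 5; 300 runs) rejected in 94%, 41% and 5.7% of runs for the three rows. With equal correction (0.40 vs 0.40), rejection is about 5% whichever scoring is used.

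Dropping the index order alone is therefore not enough. The scoring time has to change as well.

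**The case against.** **The scoring time and the handling of the index order are not stated.** This is true. The start of the set could mean orders placed after the first alert, and the Section 9.3.1 outcome cannot carry over unchanged to patients who never had an alert. The reading used here is an inference from the outcome being receipt, the reference back to the earlier model, and the lack of any exclusion. If scoring at first entry was intended, the text still needs to say so.

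**The closing sentence asks about total improvement.** That is a valid randomised comparison and may stay. But the paragraph is headed as carry-over and introduced as exploring future errors avoided, which a total effect cannot isolate.

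**Other parts of the plan come close.** Reach and Maintenance (8.2, 9.3.4) count alerts fired and revisit outcomes at 6, 12 and 18 months. Neither states an Alert 1 vs 2 comparison of errors at order entry, and nor does the time series.

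**The gap between alerts may be small.** This stands. The alerts differ only in a consult button, pharmacy consults are always available (1.1), and the documents give no correction rates for alerts. The sizes above are illustrations.

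**A reader might infer that the analysis will show learning whether or not there is any.** The documents do not support that: with equal immediate correction there is no false signal. Nor do they show that the sponsor would report a difference as lasting education.

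**Conclusion.** The point holds in a conditional form. As naturally read, the analysis estimates the direct effect plus any carry-over and cannot separate the two. With no learning, it differs between arms whenever the alerts differ in immediate correction, which is the trial's own hypothesis (Section 4.1). Under the assumptions above (10% entry error, 10 later orders, 40% vs 60%), the difference is 3.6 points with the index order and 2 points without. It scales with the gap between the alerts. The correction rates for alerts, the entry error rate and the number of later orders are all assumed.

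The weight is limited. This is a sensitivity analysis in the exploratory section, and the primary and secondary comparisons are unaffected. It is still worth changing, because the wording leaves the analysis unable to answer the question it sets.

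**What to change.** In Section 9.3.5:

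- Define the carry-over outcome as whether a new order, as first entered, triggers a study DOAC alert (yes/no), before any response to that alert.
- Use as denominator each prescriber's new orders after the index order for the two drugs the alerts cover, apixaban and rivaroxaban (1.1). Section 2.1 lists four DOACs; orders for the others should not be counted if they cannot trigger a study alert.
- Exclude the index order and any replacement order placed in response to an alert. The sample alert in Figure 2 lets the prescriber remove an order and place another; counting those replacements would let some of the direct effect back in.
- Compare Alert 1 with Alert 2 using the same prescriber random effect.
- Keep the existing overall proportion only if it is labelled the combined direct plus carry-over effect.

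The cost is a change of SAP wording, the loss of the index and replacement orders, and a little more EHR data handling to identify replacements. Alert firings and total DOACs prescribed are already planned EHR data (1.3, 9.3.5). Power for the new outcome has not been worked out here, since the number of later orders per prescriber is not in the documents.

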### 9.3.5 EXPLORATORY ANALYSIS

#### **Interrupted time-series analyses** (comparison to usual care).

While our trial and analyses are designed to determine the best approach for improving evidence-based DOAC prescribing through EHR alerts via comparative effectiveness analyses, observational analyses can also evaluate the impact of the introduction of the DOAC EHR alert system overall on patient receipt of evidence-based DOACs, relative to prior to the trial. Using EHR data, we will compute the proportion of patients that were receiving an inappropriate DOAC for each quarter, starting 24 months prior to randomization and continuing 18 months after randomization. Interrupted time series analyses (ITSA) will then be used to compute the change in inappropriate DOAC prescriptions, pre- and post-system introduction, to determine whether the system implemented via the trial resulted in a significant decline in patients on inappropriate DOACs. We will also assess for system-level changes in adverse event rates, as defined in the Measures section. As a further check on changes in DOAC prescribing behaviors in response to the alerts and/or increased prescriber-pharmacist collaboration, we will also use ITSA models to assess for changes in the rate of new-prescription alerts (per total number of DOACs prescribed) over the 18-month study period, relative to the 24-month period prior to study start.

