#### **Moderator analyses.**

Moderator analyses will be used to help pinpoint the prescriber- and patient-characteristics that most benefit from alerts designed to facilitate prescriber-pharmacist collaboration for both the new-prescription alerts and existing-prescription notifications. We hypothesize that for both new-prescription alerts and existing-prescription notifications, alerts and notifications that engage pharmacists will be more effective at improving patient receipt of evidence-based DOACs for prescribers that (1) are based in primary care vs. medical specialists and/or (2) have prescribed fewer DOACs in the six months preceding randomization; and for patients that (1) are aged 70+; (2) have a VTE (as opposed to AF) diagnosis, as the former has more complex dosing that many clinicians are less familiar with; (3) have 5+ concurrent medication prescriptions; and/or (4) have moderate or worse renal function (creatinine clearance  $\leq 60$  ml/min). Moderators will be assessed by adding interaction effects between the treatments and the moderator(s) of interest to the primary analysis model described above. All tested moderators will be reported and those that show both clinical and statistical significance will be considered for use in tailoring alert delivery.

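### The exploratory carry-over analysis does not pre-specify adjustment for each prescriber's pre-randomisation prescribing record, giving up a little precision but no validity

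*Combined protocol and SAP*

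**What the plan says.** The carry-over paragraph under Sensitivity analyses in section 9.3.5 asks whether an alert with a pharmacist-referral option teaches prescribers to avoid later errors. It will "evaluate the main effect of the two new-prescription alerts on the proportion of DOAC patients that receive a new prescription for an evidence-based DOAC". The main model is reused, applied to everyone for whom the prescriber orders a DOAC during a window defined as "from the point they received their first new-prescription alert through the end of the 18-month study period". The stated aim is: "This will allow us to evaluate whether correct DOAC prescribing improved overall by type of new-prescription alert".

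The model referred to is in section 9.3.1: mixed-effects logistic regression with the two treatment factors, their interaction and a prescriber random effect, "as well as any stratification variables and baseline patient- and/or prescriber-level characteristics that are unbalanced". Section 6.3 stratifies prescribers as trainee, non-trainee specialist or non-trainee primary care. No measure of earlier prescribing is a stratum or a named covariate.

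Pre-trial data appear in two other parts of section 9.3.5. The interrupted time series uses quarterly system-level proportions, "starting 24 months prior to randomization and continuing 18 months after randomization", and compares the rate of new-prescription alerts during the trial with the preceding 24 months. One moderator is whether prescribers "have prescribed fewer DOACs in the six months preceding randomization". That is volume, not appropriateness.

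**The concern.** In a randomised comparison, the precision gained from a baseline covariate depends on how well it predicts the outcome, not on whether the arms happen to differ on it. Under the section 9.3.1 rule, a strongly predictive but well-balanced covariate is left out. The rule also leaves the choice until after the arms have been inspected, and gives no list or threshold.

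A prescriber's past rate of evidence-based prescribing is the obvious predictor of the later rate. The carry-over analysis is also where it could help most. The main analyses expect about 2 alert-triggering patients per prescriber (section 9.1), whereas the carry-over analysis takes in every patient to whom the prescriber gives a DOAC after the first alert. With larger clusters, differences between prescribers make up more of the noise.

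At stake is how sharply the trial can say whether the referral alert has a learning effect. The time series cannot answer that, because it is observational and does not separate the alert types. A second, smaller matter is wording: with only post-alert data in the model, improvement has no pre-trial reference.

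**Working it through.** **The plan's own figure.** Section 9.1 gives 80% power for 40% vs 52% with 300 prescribers, 2 patients each, ICC 0.1 and alpha 0.05. Effective n per arm = 150 × 2 / (1 + 1 × 0.1) = 272.7. A two-sided two-proportion test with pooled variance gives 80.5%, so the figure reproduces. The plan states no power or precision for the carry-over analysis.

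**Inputs**
- From the documents: 150 prescribers per alert, ICC 0.1 for the main outcome, alpha 0.05 (two-sided assumed).
- Assumed: m1 = 5, 10 or 20 new DOAC prescriptions per prescriber in follow-up; m0 = 7, 13 or 27 in the pre-period (m1 × 24/18, rounded); correlation ρ = 0.8 between a prescriber's true pre and post rates; 88% vs 92% as the effect.

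**Which ICC.** The 0.1 is planned for an outcome at 40% to 52%. The carry-over outcome is likely to be near 90%: section 2.1 reports 7.2% of patients clearly outside guidelines in a one-day snapshot. On the proportion scale, ICC = Var(p) / [P(1 − P)], where P is the mean rate and the prescribers' log-odds are normal with SD σ.
- ICC 0.1 at P = 0.46 (midpoint of 0.40 and 0.52) implies σ ≈ 0.70. The same σ at P = 0.90 gives an ICC of about 0.046.
- If 0.1 is read on the latent logistic scale, σ = √(0.1/0.9 × 3.29) ≈ 0.605, and the ICC at P = 0.90 is about 0.034.

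**Formulas**
- Reliability of a prescriber's rate: R(m) = m·ICC / [1 + (m − 1)·ICC]
- Share of variance removed: r² = ρ² × R(m1) × R(m0)
- Effective n per arm: 150·m1 / [1 + (m1 − 1)·ICC], divided by (1 − r²) after adjustment

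Worked case, ICC 0.046, m1 = 10, m0 = 13: R = 0.325 and 0.385; r² = 0.64 × 0.325 × 0.385 = 0.080. Effective n rises from 1500/1.414 = 1061 to 1061/0.920 = 1153, and power from 86.7% to 89.3%.

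| ICC | m1 / m0 | Variance removed | Power, 88% vs 92% |
|---|---|---|---|
| 0.034 | 5 / 7 | 2% | 67.9% → 68.7% |
| 0.034 | 10 / 13 | 5% | 89.2% → 90.7% |
| 0.034 | 20 / 27 | 13% | 98.1% → 99.1% |
| 0.046 | 5 / 7 | 3% | 66.1% → 67.4% |
| 0.046 | 10 / 13 | 8% | 86.7% → 89.3% |
| 0.046 | 20 / 27 | 18% | 96.5% → 98.6% |
| 0.1 | 5 / 7 | 10% | 58.8% → 63.3% |
| 0.1 | 10 / 13 | 20% | 75.5% → 84.2% |
| 0.1 | 20 / 27 | 33% | 85.9% → 96.0% |

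The variance removed scales with ρ². At ρ = 0.6 the first six rows are multiplied by 0.36/0.64 = 0.56, giving about 1% to 10%.

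**Larger panels.** Section 2.1 gives a median of 23 DOAC patients per prescriber (IQR 7 to 47). That counts all documented users on one day, not new prescriptions, so it is only a loose guide. A simulation with σ = 0.605, binary outcomes and unequal panels gave reductions of about 3% to 14% at a median of 7, and 10% to 29% at a median of 23, for correlations of 0.5 to 0.9.

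**The case against.** The strongest reply is that nothing is broken. The analysis compares randomised arms, which needs no baseline to be unbiased, and a reference to improvement by alert type reads naturally as a between-arm difference. Change over time is handled at system level by the time series. The analysis is exploratory, has no power target, and supports no primary or secondary conclusion. All of that stands.

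The reply also limits the size. The calculations compare adjustment with no covariates at all, while the model already includes the strata. Prescriber type plausibly predicts error, so part of the computed gain is already secured.

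Three stronger readings are tempting, and the documents do not support them. A reader might infer that the plan excludes prescribers' earlier records; section 9.3.1 would admit such a characteristic if it were unbalanced. A reader might infer that each prescriber's prior appropriateness rate is already in use; the time series is system level and the moderator uses volume only, so the rate would have to be built. A reader might infer from the plan's ICC of 0.1 that a real learning effect is likely to be missed; that carries an ICC from an outcome at 40% to 52% to one near 90%, where the same spread between prescribers gives less than half of it.

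What survives is narrow. The imbalance trigger is the wrong criterion for a covariate whose value lies in prediction, and most of the data needed are already to be extracted.

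**Conclusion.** The point holds as a modest matter of efficiency. The carry-over model does not pre-specify a prognostic covariate that can be derived from planned data, and its rule for admitting one looks at balance instead of prognosis. The cost is precision only. Improvement should be read as a difference between the alerts, not as change from the pre-trial level.

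Under the working assumptions (ICC 0.034 to 0.046, ρ = 0.8, 5 to 20 new prescriptions), about 2% to 18% of the variance is removed and power rises by about 1 to 3 points, before credit for the strata. Larger panels or a higher correlation would raise the gain; a lower correlation would reduce it. The 10% to 33% obtained with an ICC of 0.1 on the proportion scale is an optimistic upper case for 5 to 20 prescriptions. The documents give none of these inputs for this outcome, so every figure is illustrative. Priority: optional, low-cost improvement to an exploratory analysis.

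**What to change.** In the carry-over paragraph of section 9.3.5, name one covariate to be included whether or not the arms look balanced: each prescriber's proportion of evidence-based new DOAC prescriptions in the 24 months before randomisation. Specify that:
- the current alert logic is applied to the stored orders;
- the proportion is shrunk toward the overall mean, so that low-volume prescribers do not add noise;
- a missing-history indicator is used for prescribers with no pre-period, such as new house officers.

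Add a sentence saying that improvement here means a difference between the alert arms.

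The cost is SAP wording and modest data work. The time series already needs pre-trial new-prescription alert rates. Section 2.2.2 says the only existing DOAC prescribing alerts concern drug-drug interactions, so that series appears to need the logic run over past orders anyway. The added step is to attribute those orders to individual prescribers. No new patients or procedures are needed. The gain will be small for prescribers who write few DOAC prescriptions.
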